Protocol approved: July 16, 2020

Study Title: Transcranial random noise stimulation (t-RNS) After Hand Recovery in Chronic Stroke

Clinical Trials.gov ID: NCT05489146

STUDY PROTOCOL

This is a double-blind pilot randomized control study. Individuals with moderate-to-severe stroke were randomly allocated to two groups:

Screening procedures

After obtaining the informed consent, potential participants were screened in more detail using a medical chart review and standardized clinical assessments.

Participants were recruited through referrals from the UPMC Rehabilitation Institute, UPMC Centers for Rehab Services, and the University of Pittsburgh Stroke Rehabilitation Research Network.

The following procedures were administered to screen potential participants:

- 1) We reviewed potential participants' medical charts after obtaining informed consent to confirm they have a primary diagnosis of unilateral hemiparesis due to a single episode of stroke, are 18 years or older, and that their onset of stroke is at least 6 months prior to study screening, have no history of schizophrenia, other neurological or medical conditions that would confound results.
- 2) We conducted a brief screen of upper extremity range of motion using a goniometer to determine if individuals are able to actively flex and extend the more-affected shoulder and elbow at least 30°.
- 3) We asked participants to follow directions to determine whether they have the ability to follow 3-step commands.
- 4) We conducted a brief cognitive screen using Mini Mental Status Examination to screen for cognitive impairments which may confound the results of the study.
- 5) We also conducted a brief mood screen using Patient Health Questionnaire-9 to screen for more than mild depression and question 16 and items of the (hypo) maniac module of the Mini-International Neuropsychiatric Interview Hybrid Assessment to screen for bipolar disorders.
- 6) We screened for one side neglect or hemispatial neglect using the Line Bisection Test, which is a quick paper-pencil test.

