We provided adequate rest breaks during the treatment if the patients feel tired during the treatment. Participants will only use the FES during research treatment. The Neuromove and the Starstim devices were not given to participants for their in-home use between the investigator's interventions. Participants also completed a tRNS and FES side effects questionnaire immediately after each treatment session.

Control Group: Functional training with FES with sham tRNS

The control group underwent similar functional training with FES but received sham tRNS.

Sham tRNS was delivered using the Starstim device. All the procedures of applying the electrodes and checking the impedance were the same for sham stimulation as well. During the stimulation, participants experienced a gradual ramp-up of the low-intensity current stimulation for the 1st minute, which gradually faded away after the 1st minute and participants did not receive any stimulation for the rest of the session.

We provided adequate rest breaks during the treatment if the patients felt tired during the treatment. Participants only used the FES during research treatment. The FES was not given to participants for their in-home use between the investigator's interventions.

All intervention sessions in both the experimental and control groups were videotaped. We randomly examine 15% of sessions in both groups and assess fidelity based on pre-defined principles.

Procedures to prevent interference between the devices:

In addition, all cables from the electrodes of the Starstim device are encased in a small unit that securely attaches to the participant's back of the head. This small unit then wirelessly communicated with the software on the computer. Thus, there were no hanging cables from the Starstim device.

Also, the electrodes of the Neuromove device are directly connected to the Neuromove device and are securely attached to the forearm muscles. Therefore, the two devices are never in direct contact, which will prevent any interference including leakage of current from the portable devices or leads during active treatment.

Procedures to monitor and recognize excessive cortical excitability:

During the treatment: The starstim has an in-built feature, which shuts automatically shuts off if the skin impedance is more than 2 kOhm.

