Immediately after treatment: We will ask the participants to complete a tCS side effects questionnaire (attached) to document any side effects and provide adequate treatment if required.

POST-INTERVENTION ASSESSMENT

The assessments, which were administered pre-intervention were administered within one week after the completion of the intervention.

POST-2 (FOLLOW-UP) INTERVENTION ASSESSMENT

We administered the assessments again three months after the completion of the intervention.

STATISTICAL ANALYSIS

Linear mixed model analyses were used to test the added benefits of tRNS on upper-extremity function after stroke. This analysis was performed both for the primary (Fugl Meyer Upper Extremity Assessment) and secondary (grip strength, Wolf Motor Function Test, and hand subscale of stroke impact scale) outcome measures. The participant's group (tRNS, sham-tRNS), time (PRE, POST, POST-2), and group x time interaction were entered as the fixed independent variables along with baseline scores on the respective outcome measures as covariates in the model. Subject was included as a random effect in the model. A significant main or interaction effect was followed by post-hoc analyses using the Sidak multiple comparison procedure. An alpha level of $P<0.05$ was considered significant for all tests.

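### Post-hoc comparisons depend on a significant F test, and no tRNS-minus-sham difference with a confidence interval is planned at POST or POST-2

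*Combined protocol and SAP*

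**What the plan says.** The opening of the Study Protocol describes the trial: "This is a double-blind pilot randomized control study". The Statistical Analysis section gives the purpose of the analysis: "Linear mixed model analyses were used to test the added benefits of tRNS on upper-extremity function after stroke". For the fixed effects, group is entered together with "time (PRE, POST, POST-2), and group x time interaction were entered as the fixed independent variables along with baseline scores", and "Subject was included as a random effect in the model". The same model serves the Fugl Meyer Upper Extremity Assessment (FMUE, primary) and three secondary outcomes.

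The only stated route from the model to specific comparisons is: "A significant main or interaction effect was followed by post-hoc analyses using the Sidak multiple comparison procedure". The threshold is stated as: "An alpha level of $P<0.05$ was considered significant for all tests".

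The section names no tRNS-minus-sham contrast, no primary time point and no confidence interval. It does not say which comparisons follow which significant effect. It also does not say that model estimates are withheld when the tests miss 0.05.

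**The concern.** What a pilot can usefully pass on is the size of the treatment difference and its uncertainty. The differences of interest are those at POST and POST-2, and the only planned step that would compare the arms at those visits is the conditional one. An estimate reported only when a test of the same effect is significant is too large on average whenever power is well below 1.

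Two harms could follow. A small trial that misses 0.05 could be read as showing no added benefit, although moderate benefits remain compatible with the data. A trial that reaches 0.05 could pass on an exaggerated FMUE difference, and a later trial sized on it would be too small. This is bias in an estimate when a true effect exists. It is separate from the false-positive rate of the F tests.

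**Working it through.** **Inputs from the documents.** Two groups, three visits, the model above, and alpha 0.05. There is no sample size, SD, correlation or effect size, so there is no stated figure to reproduce.

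**Assumed inputs.** 1:1 allocation; 8 to 20 per arm; SD of POST FMUE given baseline 4 points; correlation 0.6 between POST and POST-2 residuals; true benefit 2 or 3 points at both later visits. The planned model was simulated with split-plot F tests, 3,000 trials per setting.

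**Reading A: group contrasts follow a significant group or interaction effect.** Inflation is the mean POST estimate in the selected trials divided by the true value.

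| True benefit | n per arm | Contrast triggered | Mean POST estimate when triggered | Inflation |
|---|---|---|---|---|
| 2 | 8 | 21% | 4.18 | 4.18/2 = 2.1 |
| 2 | 10 | 25% | 3.87 | 3.87/2 = 1.9 |
| 2 | 15 | 35% | 3.31 | 3.31/2 = 1.7 |
| 2 | 20 | 42% | 3.01 | 3.01/2 = 1.5 |
| 3 | 8 | 37% | 4.64 | 4.64/3 = 1.5 |
| 3 | 10 | 46% | 4.28 | 4.28/3 = 1.4 |
| 3 | 15 | 61% | 3.77 | 3.77/3 = 1.3 |
| 3 | 20 | 73% | 3.47 | 3.47/3 = 1.2 |

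No contrast is triggered in 100 − 73 = 27% to 100 − 21 = 79% of trials. Without selection, the same estimate averages 1.99 to 2.01 (true 2) and 2.97 to 2.99 (true 3). If only the interaction opens the step, selection is slightly harsher: at 8 per arm with true 2, it opens in about 15% of trials and the mean is about 4.4.

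**Reading B: any significant effect, including time, triggers the group contrasts.** This adds an assumed 2-point gain in both arms.

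- 8 per arm, true 2: opens in 87 to 88% of trials; mean about 2.05.
- 10 per arm, true 2: opens in 94%; mean 2.05.
- 20 per arm, true 3: opens in about 100%; mean about 3.0.

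With no shared gain, inflation at 8 per arm and true 2 is about 1.6, against 2.1 under Reading A.

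**Check on other assumptions.** SD 1 at each visit, within-subject correlation 0.8, 10 per arm, true difference in change 0.3 SD, 8,000 trials. Reading A opens in 27% with inflation about 1.8. Reading B with a shared 0.5 SD gain opens in about 100% with ratio 0.98; with no shared gain it opens in 39% with inflation about 1.5. The pattern is the same.

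**What the ungated model gives.** PRE is a level of time, and before treatment the expected group difference is 0. For a benefit d at both later visits, the group main effect is (0 + d + d)/3 = 2d/3: 1.33 points for d = 2, and 2 points for d = 3. The POST difference has to be built from the group and interaction coefficients, and the plan does not ask for this.

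**Precision that would be reported.** In the SD-unit setting, the SD of change is √(2 × (1 − 0.8)) = √0.4, and the 95% half-width is t × √0.4 × √(2/n), with t on 2n − 2 degrees of freedom. This gives 0.92, 0.59, 0.47 and 0.40 SD at 5, 10, 15 and 20 per arm. Intervals this wide would themselves warn against reading a P value above 0.05 as no benefit.

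**The case against.** The strongest objection is that the quoted rule covers any main effect, and time is the one most likely to be significant. Both arms train with FES: "The control group underwent similar functional training with FES but received sham tRNS". On the literal wording, the comparisons would then nearly always be run and the selection bias would nearly vanish, as Reading B shows. This stands as far as it goes. Against it, post-hoc tests usually break down the effect that was significant, so a time effect would lead to comparisons between visits, which say nothing about tRNS versus sham. The text settles neither reading.

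Second, the model is fitted to every outcome without any gate and gives group and interaction coefficients with standard errors whatever the P values. This also stands. A reader might infer that the pilot must yield either no effect estimate or an exaggerated one, or that its only output after a null test is the words not significant. The documents do not support that: they are silent on reporting the coefficients and do not exclude it. What remains is that no visit-specific difference is planned, and that the most visible coefficient, the group main effect, is diluted.

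Third, the documents do not say that a later trial will be sized on this estimate, or that a null result will be read as no benefit. Those harms are possible, not planned.

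**Conclusion.** The point holds in conditional form. The post-hoc comparisons depend on significance, and no tRNS-minus-sham difference with a confidence interval is planned at POST or POST-2. If between-group contrasts follow only a significant group or interaction effect, the visit-specific contrast may be missing or inflated by about 1.2 to 2.1 times under the assumptions listed. If a significant time effect also triggers them, inflation is smaller, and close to nil when both arms improve.

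These sizes are illustrative, because every input except alpha and the model structure is assumed. Certain bias, or the absence of any estimate, cannot be concluded from the text. The case for the change rests on the missing unconditional estimate and the unresolved reading, not on a particular inflation factor.

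**What to change.** Replace the sentence on post-hoc analyses with:

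> The baseline-adjusted tRNS minus sham difference at POST and at POST-2 is reported with its 95% confidence interval for every outcome, whatever the F tests show; a P value above 0.05 is not read as absence of benefit.

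This removes the selection under either reading and makes the ambiguity about the time effect irrelevant to the treatment estimate. It needs no new data and no different model, since both differences are combinations of coefficients already fitted. The section is written in the past tense, but the estimates can still be included in, or added to, the report. The only downside is a longer results table.
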